9.1 Primary Efficacy Analysis

The primary endpoint of our study is to examine the efficacy of a Physical Therapistadministered physical activity intervention and standardized outpatient PT to increase MVPA over 6 months after discharge from outpatient PT compared to a control group that received standardized outpatient PT.

The statistical model underlying this analysis is a mixed-effects model to examine the main and interaction effects of *group* (Intervention vs. Control) and *time* (BL, DC, and 6M) on MVPA (minutes/day). We will adjust this model for age, sex, and body mass index.

9.2 Secondary Efficacy Analyses

9.2.1 Secondary Analyses of Primary Efficacy Endpoint

The per protocol sample, instead of the ITT sample will be used for the analysis of the primary efficacy endpoint.

9.2.2 Analyses of Secondary Endpoints

The secondary analyses endpoint of our study is to examine the efficacy of a Physical Therapist-administered physical activity intervention and standardized outpatient PT to increase MVPA over 12 months after discharge from outpatient PT compared to a control group that received standardized outpatient PT. We also examined the number of Steps/day over 6 and 12 months. The statistical model underlying this analysis is a mixed-effects model to examine the main and interaction effects of *group* (Intervention vs. Control) and *time* on MVPA (minutes/day) and Steps/day in separate models. We will adjust these models for age, sex, and body mass index.

9.3 Exploratory Efficacy Analyses

We will explore possible statistical interaction of study group with age (< and \geq 65 years), obesity (< and \geq 32 kg/m2), and sex (male/female) in separate analysis.

10 Safety Analyses

- All-Cause Mortality: A table of all anticipated and unanticipated deaths due to any cause, with number and frequency of such events in each arm/group of the clinical study.
- Serious Adverse Events: A table of all anticipated and unanticipated serious adverse events, grouped by organ system, with number and frequency of such events in each arm/group of the clinical study.
- Other (Not Including Serious) Adverse Events: A table of anticipated and unanticipated events (not included in the serious adverse event table) that exceed a frequency threshold (for example, 5 %) within any arm of the clinical study, grouped by organ system, with number and frequency of such events in each arm/group of the clinical study.

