5.2 Endpoints

The primary endpoint of our study is to examine the efficacy of a Physical Therapistadministered physical activity intervention and standardized outpatient PT to increase MVPA over 6 months after discharge from outpatient PT compared to a control group that received standardized outpatient PT.

The secondary analyses endpoint of our study is to examine the efficacy of a Physical Therapist-administered physical activity intervention and standardized outpatient PT to increase MVPA over 12 months after discharge from outpatient PT compared to a control group that received standardized outpatient PT. We will examine the number of steps/day over 6- and 12- months. Lastly, we will examine as an exploratory analysis to what extent baseline characteristics and treatment condition interact with study outcomes (MVPA and steps/day).

6 Study Methods

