6.2 Inclusion-Exclusion Criteria and General Study Population

(ICH E3;9.3. ICH E9;2.2.1)

We recruited individuals who met the following inclusion criteria: 1) aged 45 years or older, 2) seeking outpatient physical therapist services for a unilateral TKR, and 3) were interested in increasing their PA. We excluded individuals who 1) had any comorbidities that made it unsafe for them to engage in PA, as instructed by a physician; 3) had a lower extremity surgery in the 6 months prior to study enrollment, or were planning a surgery in the 6 months after study enrollment; or 4) previously received a PA intervention at the Delaware Physical Therapy Clinic.

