6.4 Study Assessments

(ICH E3; 9.5.1. ICH E9; 2.2.2)

Visit Description	Patient Eligibility Screen and Enrollment	Randomization		Discharge	Follow-up Period	
Study visit: Study Day (Range of assessment periods)	Visit 1: Day 0 (+/- 14 days)	Visit 2: Day 7 (-2, +8 days)	Treatm ent Period ¹	Visit 3: Day² (-14, +30 days)	Visit 4: 180 Days after Discharge (6 month) (-30, +60 days)	Visit 5: 360 Days after Discharge (12 month) (-30, +60 days)
Informed Consent/HIPAA	х					
Demographics/ Medical History	x					
Accelerometer	Х			Х	Х	Х
Randomization		Х				
Adverse Events			Х	Х	Х	Х
 1 – Study intervention will be delivered when the study participant visit PT. The total number of visits will be based on the number of PT visits during the PT episode of care. The number of visits will be based clinically on physical therapist discretion in accordance with standard physical therapy guidelines. 2 – The study visit day varies depending on the duration of outpatient PT 						

Data collected outside of the time windows listed above will be classified as the intended visit the data was to reflect and noted as being outside the time window. Such data will be included in the primary analyses, however we will also perform a secondary analyses excluding data collected outside the time window.

Study Variable	Description	Endpoints	Interpretation	
Age	Age of study participant in years	Minimum 45 years	N/A	
Gender	Self-reported Sex of study participant	Male/Female	N/A	
BMI	Body Mass Index calculated from weight and height.	Body Mass Index calculated from weight and beight		
Race	Self-reported race	Self-reported race White, Black or African American, Asian, American Indian or Alaskan Native, Hawaiian, more than one race, other		
Hispanic	"Do you consider yourself to be Hispanic or Latino?"	Yes/No	N/A	
Health History Questionnaire	The number of comorbidities from a list of 54 possible conditions	N/A	N/A	
Moderate to Vigorous intensity Physical Activity (MVPA)	MVPA calculated from a monitor (ActiGraph GT3x)	Continuous measure. Minimum value 0 minutes/day	Higher values indicate greater time in MVPA	
Steps/Day	Steps/day calculated from a monitor (ActiGraph GT3x)	Continuous measure. Minimum value 0 steps/day	Higher values indicate greater steps taken/day	
Adverse Event	Defined as any unfavorable or unintended diagnosis, sign, symptom, or disease that is associated with the study and that may or may not be related to the intervention.	Continuous number of adverse events	N/A	

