7.3 Covariates and Subgroups

(ICH E3; 9.7.1, 11.4.2.1. ICH E9; 5.7)

We have identified three covariates that are expected to have an important influence on our study outcomes, i.e., age, sex, and body mass index. We will adjust for these covariates in all analyses. In particular, age and body mass index will be treated as continuous variables, and sex as a categorical variable. We will perform separate subgroup analyses to examine evidence for a difference in treatment effects based on 1) Age (< and \geq 65 years), 2) Sex (men and women), and 3) BMI (< and \geq 32 kg/m2).

SAP version 1.0: Physical Activity Intervention after TKR 3/16/23

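### Exploratory tests of effect modification by age and BMI use only two-level versions of variables held as continuous; if the variables are roughly normal and the modification linear, about a third or more of the information is lost

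*SAP*

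**What the plan says.** SAP 5.2 lists effect modification last among the endpoints: "we will examine as an exploratory analysis to what extent baseline characteristics and treatment condition interact with study outcomes", the outcomes being MVPA and steps/day. Two later sections describe how.

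- **SAP 9.3** (exploratory efficacy): "We will explore possible statistical interaction of study group with age", obesity and sex. Age is cut at 65 years and obesity is defined by BMI at 32 kg/m2.
- **SAP 7.3** (covariates and subgroups): "We will perform separate subgroup analyses to examine evidence for a difference in treatment effects", with the same three variables and the same cuts. It names no interaction term.

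The data are finer than the cuts. The variable table in SAP 6.4 defines age as "Age of study participant in years" and BMI as "Body Mass Index calculated from weight and height". For covariate adjustment, 7.3 states that "age and body mass index will be treated as continuous variables, and sex as a categorical variable". Neither section plans an interaction with age or BMI on the continuous scale, and neither explains the choice of 65 or 32.

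**The concern.** The mixed model already carries age and BMI as continuous. Reducing each to two levels for the interaction alone treats a participant just above the cut like one far above it. If the treatment effect changes gradually with age or BMI, the test loses power, and an exploratory look at modifiers in a trial of 120 has little to spare.

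Two points of wording add to this. SAP 9.3 speaks of interaction with study group and does not mention time. In this model baseline is one of the time points and the null hypothesis (SAP section 9) concerns change in MVPA, so the treatment effect is the group x time term. Modification of that effect is therefore group x time x modifier. The SAP names neither the time point nor the estimate to be reported for it. In addition, 7.3 can be read in more than one way on whether its subgroup analyses are interaction tests.

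**Working it through.** **Inputs from the documents.** N = 120 (SAP section 7). Age in years and BMI from weight and height (SAP 6.4). Age limited to those "aged 45 years or older" (SAP 6.2). Cuts at 65 years and 32 kg/m2 (SAP 7.3 and 9.3). Two-sided p-values (SAP section 9). The SAP gives no power, effect size or SD, and no figure at all for the interaction tests, so there is no stated figure to reproduce.

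**Assumptions.** Alpha 0.05, 1:1 allocation, linear modification, and the distributions of age and BMI shown below.

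**Formula.** If the effect changes linearly with a modifier X, an interaction test on the indicator D = 1[X >= c] keeps a fraction corr(X, D)^2 of the information in the test on X itself. For a normal X with a proportion p on one side of the cut and z the matching normal quantile, this is phi(z)^2 / (p(1-p)).

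| Split (normal X) | Kept | Lost | 120 act like |
|---|---|---|---|
| 50/50 | 0.637 (= 2/pi) | 36.3% | 120 x 0.637 = 76 |
| 70/30 | 0.576 | 42.4% | 120 x 0.576 = 69 |
| 80/20 | 0.490 | 51.0% | 120 x 0.490 = 59 |

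The median split is the best case for a normal modifier. Matching the continuous test would then take 120 / 0.637 = about 189 participants.

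**Power.** A continuous test with 80% power has a noncentrality of 1.960 + 0.842 = 2.802. After a median split, power is Phi(2.802 x sqrt(0.637) - 1.960) = about 61%. A simulation at N = 120 (10,000 runs) gave 77% for the continuous term and 57% for the split.

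**Other shapes.**

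- Age normal but truncated at 45, cut at 65, assumed mean 60 to 70 and SD 6 to 10: loss 34% to 51%.
- BMI cut at 32, assumed mean 29 to 35 and SD 5 to 7: loss 36% to 44% if normal, 37% to 49% if lognormal.
- Uniform modifier cut at its midpoint: on (0, 1) the covariance of X and D is 1/8, so (1/8)^2 / ((1/12)(1/4)) = 0.75 is kept. The loss is 25%, 120 act like 90, and 80% power falls to Phi(2.802 x sqrt(0.75) - 1.960) = about 68%. Age uniform on 45 to 80 and cut at 65 loses 26.5%.
- True step exactly at the cut: D is the correct form and nothing is lost.

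**Why the wording of 7.3 deserves a line.** Suppose the trial has 80% power overall and the effect is identical in two equal halves. Each half then has power Phi(2.802 / sqrt(2) - 1.960) = 0.508. One half is significant and the other is not with probability 2 x 0.508 x 0.492 = 0.50, with no modification present. Tests within each subgroup would therefore mislead about half the time.

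**The case against.** The strongest defence is that fixed cuts are a legitimate modelling choice. They are written into the SAP, so they are not chosen from the final results, and they give effects that are easy to read by category. A linear interaction is itself an assumption: where the true modification is a threshold or is not monotone, a single linear term can lose power or miss it. That is fair as a caution. But the SAP states no threshold hypothesis at 65 or 32, and keeping the categories for display preserves the readable results.

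A reader might infer that cutting always discards at least a third of the information. The documents do not support this. They give no mean, SD or shape for age or BMI, and the loss is 25% for a uniform modifier and zero for a step at the cut. The effective counts are also illustrative, because they use all 120 participants while the analysis samples depend on wear-time criteria.

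A reader might also infer that 7.3 plans separate significance tests within each subgroup. Its stated purpose is to look for a difference in treatment effects, which is what an interaction test does. SAP 9.3 names the same variables and cuts, calls the analysis an interaction, and says it is done separately for each. The natural joint reading is one interaction analysis per modifier. No section plans a p-value within a subgroup, and no mock table shows subgroup results. What stands is that the wording leaves the other reading open.

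**Conclusion.** The point holds as an inexpensive improvement to an exploratory analysis. Age and BMI are recorded and modelled as continuous, yet their modification of the treatment effect is to be tested only on two-level versions. With roughly normal age and BMI and linear modification, the loss is about a third or more: 36% at a median split and 51% at 80/20. For age truncated at 45 it can be about 34% in the range tried. These figures rest on assumed distributions and on linearity, neither of which the documents supply.

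The discrepancy between 7.3 and 9.3 is one of wording and does not show that a wrong test is planned. It would be too much to infer that the trial's conclusions are at risk: 5.2 and 9.3 both label the analysis exploratory, and the primary and secondary comparisons of MVPA and steps/day do not depend on it.

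**What to change.** 1. In SAP 9.3, specify group x time x age and group x time x BMI in the mixed model, with age and BMI continuous, and group x time x sex, each modifier in its own model. Report the 6-month interaction with its 95% CI.
2. Keep the 65-year and 32 kg/m2 categories only to display estimated effects. They also let the reader see roughly whether a straight-line change is plausible.
3. In SAP 7.3, replace the subgroup sentence with a reference to 9.3, making clear that there is one interaction analysis per modifier and no separate significance test within each subgroup.

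The cost is a few lines of SAP text and a small code change, with no new data. The downside is the assumption of a linear interaction, which should be stated. The change is best recorded before the final analysis is unblinded.

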10.1 Adverse Events

We will report on the number of adverse events that are possibly or definitely related to the

study.

10.2 Deaths, Serious Adverse Events and other Significant Adverse Events

We will report on the number of serious adverse events and deaths that are possibly or definitely related to the study.

11 Reporting Conventions

P-values ≥0.01 will be reported to 2 decimal places; p-values less than 0.01 will be reported as "<0.01". The mean, standard deviation, and any other statistics other than quantiles, will be reported to one decimal place greater than the original data. Quantiles, such as median, or minimum and maximum will use the same number of decimal places as the original data. Estimated parameters, not on the same scale as raw observations (e.g. regression coefficients) will be reported to 2 significant figures.

12 Summary of Changes to the Protocol and/or SAP

We have modified the primary and secondary study endpoints from the original study protocol (version v.4 20 August 2018). Namely, the original study protocol listed MVPA taken at baseline, discharge, 6 months and 12 months as our primary study outcome. We have since modified this to MVPA taken at baseline, discharge, and 6 months. As well, the original study protocol listed fidelity, safety, and physical function as secondary outcomes. We have decided to investigate these outcomes in a secondary publication/manuscript separate from the primary paper. We will examine changes in steps/day as a secondary outcome in the primary paper. Lastly, we did list tertiary outcomes including self-efficacy for exercise and fear of movement in the study protocol. We will investigate these in secondary papers, and not as part of the primary paper.

13 Listing of Tables, Listings and Figures

This section is to give precise details for each table, listing or figure to be produced.

Mock Table 1: MVPA at each study time point using the ITT sample

	Baseline	Discharge	6 month	12 month
Control				
Intervention				
Control-				
Intervention				

Mock Table 2: Steps/day at each study time point using the ITT sample

	Baseline	Discharge	6 month	12 month
Control				
Intervention				
Control-				
Intervention				

Mock Table 3: MVPA at each study time point using the per-protocol sample

	Baseline	Discharge	6 month	12 month
Control				
Intervention				
Control-				
Intervention				

Mock Table 4: Steps/day at each study time point using the per-protocol sample

	Baseline	Discharge	6 month	12 month
Control				
Intervention				
Control-				
Intervention

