7.2.2 Per Protocol Sample

- All subjects who adhere to the major criteria in the protocol
 - o Subjects who did not drop out
 - Completed Physical Therapy
 - Did not drop out over the 12 months of follow up after discharge from physical therapy
 - The ActiGraph monitor was worn > 4 days at each time point (baseline, discharge, 6 months, and 12 months).

The exact process for assigning the statuses (Full Analysis Sample and Per Protocol Sample) will be defined and documented prior to breaking the blind along with any predefined reasons for eliminating a subject from a particular population.

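### SAP Section 12 defers safety to a separate paper and Section 13 lists no safety table; neither is reconciled with the by-arm harms tables planned in Section 10, and no safety population is named

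*SAP*

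**What the plan says.** - **SAP Section 12 (changes).** It records that "the original study protocol listed fidelity, safety, and physical function as secondary outcomes" and then states the present decision: "We have decided to investigate these outcomes in a secondary publication/manuscript separate from the primary paper". Although it sits in a summary of changes, this sentence is current policy, not superseded text.
- **SAP Section 13 (tables).** It opens with "This section is to give precise details for each table, listing or figure to be produced". Four mock tables follow: MVPA and steps/day, each in the ITT and the per-protocol sample.
- **SAP Section 10 (safety analyses).** It plans "A table of all anticipated and unanticipated deaths due to any cause, with number and frequency of such events in each arm/group" and also "A table of all anticipated and unanticipated serious adverse events, grouped by organ system, with number and frequency of such events in each arm/group". A third table, again by arm, covers other adverse events above a frequency threshold. No publication is named for any of them.
- **SAP Sections 10.1 and 10.2.** Section 10.1 says: "We will report on the number of adverse events that are possibly or definitely related to the" study. Section 10.2 applies the same restriction to serious events and deaths. Neither mentions arm.
- **SAP Section 7.2 (analysis populations).** Two samples are defined. The Full Analysis Sample needs valid monitor wear at baseline, discharge and 6 months, and is labelled the primary efficacy sample. The Per Protocol Sample needs no dropout and wear at all four time points. No safety sample is defined.
- **SAP Section 9.** It describes the ITT analysis differently, requiring valid wear at baseline only.

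**The concern.** The SAP describes its own objective, in Section 4.1, as that of a paper. A reader would therefore expect the Section 10 tables to appear in that paper, but Section 12 sends safety elsewhere and Section 13 provides no table for it. If Section 12 is followed, the conclusion about a step-goal intervention after knee replacement would be published on activity outcomes alone. By-arm harms would wait for a second manuscript whose timing the documents do not give.

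Two further gaps affect whichever paper carries the harms. It is unsettled whether all events or only related ones are counted, and it is unsettled who is in the denominator. Relatedness is a judgement. Participants and treating therapists know the assigned arm (SAP Sections 6.1 and 6.3), and the documents do not say that the judgement is made blind. A table restricted to related events is therefore more open to bias than a table of all events.

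**Working it through.** The point rests on comparing sections of text; the plan states no figure to reproduce.

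**1. Where safety is reported.**

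| SAP section | Content | Publication named |
|---|---|---|
| 10 | By-arm tables of deaths, serious events, other events | None |
| 12 | Safety investigated outside the primary paper | Separate manuscript |
| 13 | Four mock tables: MVPA ×2, steps/day ×2 | None (safety: 0 of 4) |

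Sections 10 and 12 can both be obeyed only if the Section 10 tables go into the second manuscript, or if descriptive counts are treated as something other than investigating safety. The SAP states neither.

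**2. Whether the missing mock table matters.** Section 13 also omits the participant flow diagram (8.1), the baseline table (8.2) and the compliance tables (8.3), so absence from Section 13 does not prove that a table will not be produced. However, 8.2 and 8.3 contain their own table layouts, whereas Section 10 describes its tables only in words. Section 7.5.4 says the principal investigator drafts mock tables for the blinded statistician to fill in. A harms table with no layout anywhere is more easily left out of that process.

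**3. Which events are counted.**

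| Event | Section 10 | Sections 10.1 and 10.2 |
|---|---|---|
| Deaths | Any cause, by arm | Possibly or definitely related; arm not mentioned |
| Serious events | All, by arm | Possibly or definitely related; arm not mentioned |
| Other events | Above a frequency threshold, by arm | Possibly or definitely related; arm not mentioned |

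These rules give different counts whenever an event is judged unrelated.

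**4. Who is in the denominator.** Take a participant with valid baseline wear who has an event and gives no monitor data at 6 months.

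- Full Analysis Sample (7.2.1): excluded.
- Per Protocol Sample (7.2.2): excluded.
- ITT as worded in Section 9: included.
- All randomised: included.

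The documents give no dropout rate. As an illustration only, assume that the 120 participants of SAP Section 7 split equally (60 per arm) and that 10% to 20% lack valid 6-month wear. Then 0.10 × 60 = 6 to 0.20 × 60 = 12 people per arm would be outside both 7.2 samples. This would affect harms only if a 7.2 sample were used for safety, which no text says. The documents do not support a figure for how many events would be lost.

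**5. Whether the fix is feasible.** SAP Section 6.4 schedules adverse events through Visit 5. The protocol adds health-status telephone calls at months 5 and 11 after discharge. Neither source depends on monitor wear. Section 7.5.3 reports that adverse events were already compared between arms at the interim.

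**The case against.** The strongest reply is that the sections can be read together. Section 12 defers fidelity in the same sentence as safety, yet Section 8.3 still tabulates Fitbit checks and recorded step goals. So the deferral may concern fuller investigation, with descriptive counts kept in the primary paper. Section 10 sits in a SAP written for a paper, and 10.1 and 10.2 say that events will be reported. This has force: Section 10 names no publication, so the sections are unreconciled rather than flatly contradictory. A reader might infer that the primary paper will certainly omit harms; the documents support only a risk of that. But the SAP does not state the reconciling reading either, and Section 12 taken literally points the other way.

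A reader might also infer that every defined analysis set removes people who stop after an event. The documents do not support this. The Section 9 ITT definition keeps anyone with valid baseline wear. The protocol (Section 7, on termination of participation) says that stopping the intervention is not leaving the study. No text applies the 7.2 samples to safety: the Full Analysis Sample is labelled for efficacy, and Section 10 counts events by arm of the study. What remains is that the safety denominator is not named and that either 7.2 sample would be a poor choice.

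**Conclusion.** The point stands as a reporting inconsistency that should be fixed before the final analysis. Three things are unresolved:

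- whether by-arm harms appear in the primary paper (Section 10 against Sections 12 and 13);
- whether all events or only related ones are counted (Section 10 against 10.1 and 10.2);
- which participants form the denominator (not stated).

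The consequence is a risk that benefit is published without harms by arm. Its size in events or participants cannot be derived from the documents. The conclusion assumes that the Section 12 sentence is current policy, which its wording supports, and that the primary paper is the one described in Section 4.1. It does not depend on any assumed dropout rate.

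**What to change.** 1. **Section 12:** remove safety from the outcomes deferred to a secondary paper. Fidelity and physical function can stay deferred.
2. **Section 13:** add one mock table for the primary paper, by arm, covering deaths, serious adverse events and other adverse events. For each, show the number of events and the number of participants with at least one event. Section 10 plans the number and frequency of events; the participant count should be stated expressly.
3. **Denominator:** state in Section 7.2 or Section 10 that the safety population is all randomised participants by assigned arm, regardless of monitor wear or dropout.
4. **Sections 10.1 and 10.2:** amend them so that all events are tabulated by arm as in Section 10, with events possibly or definitely related to the study shown as a subset.

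The cost is SAP wording and one extra table in the primary paper. No new data collection is needed, because adverse events are already scheduled through Visit 5.
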